13.5.5 Protocol Amendment 3 (Version 4.0, 17 June 2021): Summary of Major Changes

Section Number and Name	Description of Change	Brief Rationale
Section 4.2.5 – Pausing Rules	Any death due to SARS-CoV-2 infection or cases of severe SARS-CoV-2 infection will be confirmed by the DSMB as meeting pausing rules	To reduce unnecessary pausing of the study for AEs that do not meet pausing rules
	The SRC will be blinded to individual participant vaccine assignments when reviewing AEs for consideration as pausing rules	Intended to avoid bias in the interpretation of study safety data.
Section 5.1 – Method of Assigning Participants to Study Groups	Language added to address new study vaccine assignments and allowance of off-study COVID-19 vaccine	Updated to align with new study design features described throughout the rest of the document.
Section 5.2—Treatment Administration	Observer blind procedures described in greater detail	Emphasizes the importance of protecting the study blind around the time of vaccine preparation and administration
Section 5.3—Identity of Study Vaccine	The key features of each of the booster LUNAR-COV19 vaccines added	Provides a description of the latest LUNAR-COV19 vaccines entering the clinic.
	The different presentations of the priming ARCT-021 vaccine (frozen liquid) and the boosting LUNAR-COV19 vaccines (lyophilized) are highlighted	There are important differences to highlight to reduce the risk of confusion between the study vaccines.
Section 5.4—Preparation of Study Vaccine	The differences between the LUNAR-COV19 vaccines are specified.	As above.
Section 5.5.1—Study Vaccine Packaging and Storage	Each of the sets of vials of LUNAR-COV19 vaccine should be stored separately from each other in the freezer.	As above.
Section 5.8 – Blinding	Clarifies the specific windows wherein the full observer blind design is in effect and when there is a partial blind in effect.	Improved protocol comprehension
Section 5.10.1—Concomitant Therapy	Receipt of any off-study vaccine will be tracked as a concomitant therapy during this study.	Improved oversight of safety. Ensures accurate tracking of participants who have received off-study vaccination and proper analysis of relevant subgroups.
Section 5.10.2—Prohibited Concomitant Therapy	Off-study COVID-19 vaccine will be allowed	Further clarification of considerations relating to off-study COVID-19 vaccine receipt.

13.5.5 Protocol Amendment 3 (Version 4.0, 17 June 2021): Summary of Major Changes

Section Number and Name	Description of Change	Brief Rationale
Section 6 – Study Assessments and Procedures – Visits	Blood sampling will be performed prior to vaccination on vaccination visits.	Improved study interpretability
	Blood sampling for immunogenicity will only be performed under specific circumstances at unscheduled visit	Blood sampling for antibody response will only be obtained for participants being evaluated for COVID-19 disease. Antibody responses during evaluation of non-COVID-19-related AE assessment not expected to generate additional scientific value.
Section 6 – Study Assessments and Procedures – Figure 6-1	Text in footnote describing a sub-study is deleted.	Correction
Section 6.3—Immunogenicity Assessments	Blood sample added at Day 236	Correction
	Blood sampling for CMI will not be performed in re-enrolled participants	Will not increase value of the existing CMI subset analysis.
	Additional assays to evaluate immune responses to SARS-CoV-2 variants are mentioned	The study intends to better characterize vaccines and immune responses to vaccines relevant to emerging SARS-CoV-2 variants
Section 6.4.1.1.1—Adverse Events	Text added to specify that clinically significant abnormal safety laboratory assessments should be captured as unsolicited AEs.	Clarification of existing process
	Text added to further specify conditions under which a solicited AE would also be captured as an unsolicited AE	Clarification of existing process
Section 6.4.3—Clinical Safety Laboratory Assessments	Text added to specify that clinically significant abnormal safety laboratory assessments should be captured as unsolicited AEs.	As above
Section 7 – Statistical Considerations	Sensitivity analyses may be conducted.	To address issues such as administration of off-study COVID-19 vaccine.
Table 7-2	Updated to specify priming and booster vaccine-related approaches	Improved accuracy

13.5.5 Protocol Amendment 3 (Version 4.0, 17 June 2021): Summary of Major Changes

Section Number and Name	Description of Change	Brief Rationale
Section 7.3—Sample Size Determination	Text added to describe smaller sample size considerations for vaccine subgroups after booster vaccination.	Characterizes the accuracy of the planned analysis with different sample sizes that may occur following priming and booster vaccine doses. Specifically provides probability of detecting events in a subgroup with as few as 25 subjects.
Section 7.4—Analysis Sets	Reactogenicity set added	Improved precision in reporting of solicited AEs. Reactogenicity analysis set will include only subjects with data entered into daily diary to provide a more accurate denominator and percentage of participants with solicited symptoms.
Table 7-4	Sensitivity analyses may be conducted	Improves study interpretability
	Reactogenicity set mentioned	Improved precision in reporting of solicited AEs
	Analysis of booster LUNAR-COV19 vaccines described	Reflects design updates
Section 7.8—Interim Analysis	Interim Analysis 3 will include all enrolled participants and the database will be locked for the interim analysis.	Based on logistics of data availability through Day 56. Provides a more accurate description of data to be included in Interim Analysis 3 and the intent to use Interim Analysis 3 in an interim clinical study report.
	Dose selection (booster, Phase 3) based on data from previous interim analyses identified.	Latest ARCT-021 clinical data support selection of the 5- μ g dose of ARCT-021 for further evaluation in clinical trials.
Section 10.3—Data Sharing	Specified timeframe for data sharing removed. Logistics of sharing data with investigators modified	Updated for accuracy
Table 13-1 – Schedule of Events Priming Vaccinations	Updated for alignment with protocol text	Changes from the body of the protocol have been summarized in this table and footnotes.
Table 13-2 Schedule of Events Booster Vaccination	Updated for alignment with protocol text	As above

13.5.5 Protocol Amendment 3 (Version 4.0, 17 June 2021): Summary of Major Changes

Section Number and Name	Description of Change	Brief Rationale
Table 13-4 Toxicity Grading for Vital Signs	Footnote added to clarify that toxicity grading will be used when all vital sign values are analyzed, and AE severity grading scales will be used when vital signs are reported as AEs.	Improved protocol comprehension
Table 13-5 Toxicity Grading for Safety Laboratory Assessments	Footnote added to clarify that toxicity grading will be used when all safety laboratory assessments are analyzed, and AE severity grading scales will be used when abnormal safety laboratory assessments are reported as AEs.	As above

13.5.6 Protocol Amendment 4 (Version 5.0, 16 July 2021): Summary of Major Changes

Section Number and Name	Description of Change	Brief Rationale
Synopsis – Interim Analyses; Section 7.8 - Interim Analysis	Interim Analysis 3 will include all enrolled participants, Interim Analysis 4 and newly added Interim Analysis 5 will include a subset of participants, and the database will be locked prior to interim analyses 3 and 4.	Changes made to allow for a larger dataset for Interim Analysis 3 and also to perform Interim Analyses 4 and 5 with a subset of participants to inform interim reporting of study results and future clinical development planning.
Table 13-2 Schedule of Events Booster Vaccination	Updated visit window for booster dose expanded	The booster dose visit window has been expanded to increase protocol compliance.

13.5.7 Protocol Amendment 4.1 (Version 5.1, 02 August 2021): Summary of Major Changes

Section Number and Name	Description of Change	Brief Rationale
Signature Page	Removal of signature page of biostatistician	Alignment in practices for obtaining signature across Arcturus protocols
Synopsis – Interim Analyses; Section 7.8 - Interim Analysis	Interim Analysis 4 and 5 data lock points delayed by 1 month.	Changes made to allow for a larger dataset for Interim Analyses 4 and 5.
Section 5.10.2	Changed concomitant medication collection period to 28 days after each dose of study vaccine	Alignment with language in Section 5.10.1 and current data collection practices

Arcturus Therapeutics, Inc.
Protocol ARCT-021-04, Version 6.0ARCT-021
09 March 2022

Section 6.1	Figure 4 added and text clarified	Changes made to improve protocol comprehension relating to evaluation of participants with suspected COVID-19/SARS-CoV-2 exposure.
Table 13-2	Visit window for Day 208 visit changed from 3 days to +60 days	This window allows greater flexibility for scheduling the booster dose visit which is intended to increase visit compliance.

13.5.8 Protocol Amendment 5.0 (Version 6.0, 09 March 2022): Summary of Major Changes

Section Number and Name	Description of Change	Brief Rationale
Global	The protocol has been updated to reflect early termination of the study (last study visit targeted for 16 February 2022).	The Sponsor (Arcturus) has notified the health authorities of its intent to discontinue further Arcturus-sponsored studies of ARCT-021. The milestone of 16 February allows for at least 56 days of safety observation to occur for participants who have received booster vaccine doses. The study is being discontinued for strategic reasons and there are no safety concerns relating to the administration of any of the Arcturus LUNAR-COV19 vaccines.
Global	New Figure 1 added to synopsis and subsequent figures renumbered	New flow chart added to improve protocol comprehension.
Global	Number of visits reduced, specific visits or study calls will no longer be performed based on early termination	The changes reconcile study specific procedures based on early termination.
Synopsis Section 3	Endpoints updated to reflect study Early Termination status	Changes made to reflect changing of endpoint timing based on Early Termination prior to Day 570
Synopsis Section 6.3	Evaluation of cell mediated immune responses at Day 215 confirmed throughout the document for participants in the CMI subset who do not re-enroll	Changes made for consistency throughout the document
Synopsis Section 7.8	Interim analysis 4 and 5 removed	These interim analyses will no longer be performed.
Section 6.4.2	Removed requirement for COVID-19 case reporting for 12 months after last vaccination.	This reporting will no longer be performed after a participant completes study termination.
Section 7.1 Estimands and Intercurrent Events Section 7.6 Statistical Analysis Methodology	Clarified time periods for MAAE, NOCD, SAE and AEs leading to discontinuation reporting	Changes made to improve protocol comprehension regarding AE reporting time periods

Arcturus Therapeutics, Inc.
Protocol ARCT-021-04, Version 6.0

ARCT-021
09 March 2022

Section Number and Name	Description of Change	Brief Rationale
Synopsis Section 7.4 Analysis Sets	Revised to have separate analysis sets for Priming Vaccination Period and Booster Vaccination Period	Changes made to support that these two periods are summarized separately
Section 7.5 Description of Subgroups to be Analyzed	Removed on study infection subgroup.	On study infections are treated as intercurrent events instead of subgroups.
Section 7.6 Statistical Analysis Methodology	Removed sensitivity analyses	Due to the study terminating early, decision was made to focus on the primary and supportive analyses only.
Section 7.6 Statistical Analysis Methodology	Added age group to the ANCOVA model	Age group is a stratification factor for this study.
Section 7.6 Statistical Analysis Methodology	Revised to clarify intent to only list immunogenicity data for re-enrolled subjects at this time.	Change made due to decision to not summarize this data for the CSR.
Section 7.8 Interim Analyses	Removal of Interim Analysis 4 and Interim Analysis 5	Changes made due to study terminating early

13.6. OVERVIEW OF STATISTICAL METHODS: ESTIMATION OF ESTIMANDS AND SUPPORTIVE	
ANALYSES	
56	
13.7. APPENDIX 4: CLINICAL LABORATORY TESTS	59
13.8. APPENDIX 5: FDA CBER TOXICITY GRADING SCALES.....	60

List of Abbreviations

Abbreviation	Definition
ACE-2	angiotensin-converting enzyme 2 receptor
AE	adverse event
BMI	body mass index
CESI	clinical events of special interest
CFR	Code of Federal Regulations
CI	confidence interval
CMI	cell-mediated immune
COVID-19	Coronavirus Disease 2019
CRF	case report form
CRO	contract research organization
CSR	clinical study report
CTMS	Clinical Trial Management System
DSMB	Data Safety Monitoring Board
ECG	electrocardiogram
EDC	Electronic Data Capture
eCRF	electronic case report form
FDA	US Food and Drug Administration
FSH	follicle-stimulating hormone
GMFR	geometric mean fold-rise
GMR	geometric mean ratio
GMT	geometric mean titer
HIV	human immunodeficiency virus
HRT	hormone replacement therapy
IcEv	intercurrent event
ICH	International Council for Harmonisation
IFN	interferon
IgG	immunoglobulin G
IL	interleukin
IRT	interactive response technology
LLOQ	lower limit of quantification
LOD	limit of detection
MAAE	medically attended AE
MedDRA	Medical Dictionary for Regulatory Activities

Abbreviation	Definition
mITT	modified intent-to-treat
MSD	Meso Scale Discover
NAb	neutralizing antibody
NOCD	new onset of chronic disease
PBMC	peripheral blood mononuclear cells
PRNT	plaque reduction neutralizing titer
RBD	receptor binding domain
RNA	ribonucleic acid
RT-PCR	reverse transcriptase-polymerase chain reaction
SAE	serious adverse event
SAP	statistical analysis plan
SARS-CoV-2	Severe Acute Respiratory Syndrome Coronavirus 2
SUSAR	suspected unexpected serious adverse reaction
TNF	tumor necrosis factor
VAERD	vaccine-associated enhanced respiratory disease
WOCBP	women of childbearing potential

1. Introduction

This document outlines the statistical methods to be implemented in the analysis of data collected within the scope of Arcturus Therapeutics, Inc., protocol ARCT-021-04 (A Phase 2 Randomized, Observer-Blind, Placebo-Controlled Study to Assess the Safety, Reactogenicity, and Immunogenicity of the SARS-CoV-2 Vaccine ARCT-021 in Healthy Adult Participants) for the final study analysis based on Protocol Version 6.0, dated March 9, 2022.

ARCT 021 is a self-replicating RNA vaccine being developed for prevention of Coronavirus Disease 2019 (COVID-19), caused by SARS CoV 2. This is a multiregional, multicenter, Phase 2, randomized, observer-blind study designed to evaluate the safety, reactogenicity, and immunogenicity of the study vaccine in younger and older adult participants. Enrolled participants will be randomly assigned to receive either study vaccine ARCT 021 or placebo (sterile saline) as the priming vaccination series. The study also includes administration of booster doses of vaccine, which are to be given 6 months after completion of the priming vaccination series.

The PPD Biostatistics and Programming team will perform the final statistical analysis. Version 3 of the SAP outlined the final safety and reactogenicity analyses and indicated a separate analysis plan will be created for the final analysis of immunogenicity data. In order to consolidate all final analyses into one document, SAP version (Version 4) outlined all (safety, reactogenicity, and immunogenicity) final analyses. This document, SAP Version 5, contains additional clarifications to Version 4 discussed at the blinded Data Review Meeting on June 7, 2022. Separate analysis plans were created for the interim analyses. Statistical Analysis System (SAS) Version 9.4 or higher will be used. If the methods in this SAP differ from the methods described in the protocol, the SAP will prevail.

References throughout this SAP to specific visits by study day (e.g., Day 0) refer to study day as defined in schedule of events in [Appendix 1](#). Study day (also referred to as Analysis Day) is relative to the first vaccination date as:

- Day 0 is defined as the first vaccination dose
- Study Day = Assessment Date – First Vaccination Date

In order to be compliant with the Clinical Data Interchange Standards Consortium (CDISC), study day within the analysis database is calculated as Study Day = Assessment Date – First Vaccination Date + 1.

Prior to the finalization of SAP Version 3.0, Arcturus Therapeutics had determined to early terminate the study prior to the planned visits up to Day 570. In notifications sent to the Singaporean Health Authority (HSA) and US Food and Drug Administration (FDA), it was specified that final study vaccinations would conclude in December 2021 and safety would be followed through 56 days after final vaccination or February 2022, whichever came first. This decision was taken based on refocusing development efforts on other COVID-19 vaccine candidates. However, it was also recognized that due to the study participation attrition, the significant risk of receipt of other COVID-19 vaccines by participants the study may be limited in its interpretation at timepoints beyond Day 56.

2. Study Objectives and Endpoints

2.1. Primary Objectives and Endpoints

The primary objectives and endpoints are presented in Table 2-1 (For estimands, see [Appendix 3](#)).

Table 2-1 Primary Objectives and Endpoints

Objective(s)	Endpoint Descriptions
Primary	
• To assess the safety and reactogenicity of ARCT-021 compared to placebo for priming vaccination	Safety will be evaluated in all participants receiving at least 1 administration of study vaccine (ARCT-021 or placebo) and will be summarized for each vaccination as number and percentage of participants with: 
• Any unsolicited adverse event (AE) initiating within 28 days after each study vaccine administration, by severity and relationship to study vaccine• Any medically attended adverse event (MAAE), new onset of chronic disease (NOCD), AE leading to discontinuation/withdrawal or serious adverse event (SAE) through Early Termination• Safety laboratory assessment before and 7 days after each study vaccine administration, by toxicity grade Reactogenicity will be evaluated in all participants receiving at least a single administration of study vaccine and will be summarized for each vaccination as number and percentage of participants with: Any solicited local or systemic AE initiating within 7 days after each study vaccine administration, by toxicity grade

 To assess the neutralizing antibody responses of ARCT-021 compared to placebo for priming vaccination 	
Neutralizing antibody (NAb) responses will be evaluated in all participants receiving at least 1 administration of study vaccine (ARCT-021 or placebo).
 
 Geometric Mean Titer (GMT) measured at all time points Geometric Mean Fold-rise from baseline (GMFR); measured at all time points after baseline (= Day 0) Percentages of participants with ≥ 2- and 4-fold increase in titer from baseline (Seroconversion [SC]); measured at all time points after baseline GMT ratio (ARCT-021/placebo) measured at all time points

 To select the dose and schedule for use in the Phase 3 study in adult participants 	
Safety and reactogenicity data after each priming vaccine administration and immunogenicity response measured 28 days after each priming vaccination will be evaluated in younger (18 to < 56 years) and older (≥ 56 years) adults

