Overall, no trends for vaccine-related abnormalities were observed in ECGs or vital signs following vaccination with ARCT-021. Other safety laboratory assessments with patterns of interest include declining hemoglobin values (most likely due to blood sampling during trial participation), slight shifts in potassium values, and slight shifts in lymphocyte and neutrophil count. These laboratory abnormalities have been asymptomatic, and the minority have been reported as clinically significant changes.

Transient, asymptomatic lymphopenia and neutropenia have been observed with other mRNA SARS-CoV-2 vaccines ([Mulligan 2020](#); [Sahin 2020](#); [VRBPAC 2020](#)), however, lymphopenia is thought to be a normal physiological response (innate immune-stimulation-related redistribution of lymphocytes into lymphoid tissues) to immune stimulation from the vaccine ([Sahin 2020](#), [Kamphuis 2006](#)).

Immunogenicity results following vaccination with ARCT-021 showed a robust IgG immune response to the full-length SARS-CoV-2 spike glycoprotein at all doses evaluated. At doses ≥ 3 µg, GMT for PRNT50 neutralizing antibody responses tested with a clinical isolate of SARS-CoV-2 were within the range of titers observed in convalescent plasma from COVID-19 patients tested in the same assay at the same laboratory. Spike-specific T-cell responses were observed in response to stimulation with peptides from the spike glycoprotein and the CD4+ response was Th1-dominant.

The evaluation of safety data across the hundreds of participants dosed with ARCT-021 demonstrates that the vaccine leads to mild to moderate, transient AEs following vaccination for the majority of individuals. Overall AE reporting may decrease with second vaccination.

Arcturus Therapeutics, Inc.
Protocol ARCT-021-04, Version 6.0

ARCT-021
09 March 2022

Taken together, the favorable safety profile and clear signs of immunogenicity to the vaccine antigen of ARCT-021, given the fundamental similarities between the ARCT-021, ARCT-154, and ARCT-165 vaccines and, given the encouraging nonclinical data supporting immune responses to SARS-CoV-2 variants, support the continued clinical development of these three vaccines intended to prevent COVID-19.

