2.3. Exploratory Objectives and Endpoints

The exploratory objectives and endpoints are presented in Table 2-3.

Table 2-3 Exploratory Objectives and Endpoints

Objective(s)	Endpoint Descriptions
Exploratory	

 To evaluate cell-mediated immune (CMI) responses in participants receiving ARCT-021 versus placebo for priming vaccination 	
CMI responses to SARS-CoV-2 spike antigen may be measured in a subset of participants (CMI subset):
 
 Cytokine-producing SARS CoV-2 Spike protein-specific T-cells 
 as measured by flow cytometry and intracellular cytokine (Tumor necrosis factor (TNF) α, Interleukin-2 (IL-2), Interferon-γ (IFN- γ), IL-4, and IL-13) staining assay at all time points

 To evaluate safety, reactogenicity, and immunogenicity responses in participants receiving ARCT-021, ARCT-154, ARCT-165 versus placebo as booster vaccination given 6 months after priming vaccination 	
Safety:
 
 Any unsolicited AE initiating within 28 days after booster dose of study vaccine administration, by severity and relationship to study vaccine (ARCT- 021, ARCT-154, ARCT-165, or placebo) Any MAAE, NOCD, AE leading to discontinuation/withdrawal or SAE through Early Termination Safety laboratory assessment prior to and 7 days after booster vaccine administration by toxicity grade 
Reactogenicity:
 
 Any solicited local or systemic AE initiating within 7 days after booster vaccine administration, by toxicity grade 
Immunogenicity:
 
 Binding and neutralizing antibody responses (GMFR, SC, GMC, GMT, NAbs/BAbs ratio) before and after booster administration CMI responses before and after booster administration (CMI subset)

 To evaluate the incidence of confirmed COVID-19 in participants vaccinated with ARCT-021, ARCT-154, ARCT-165 versus placebo 	
Confirmed COVID-19 will be assessed in all participants starting 7 days after first study vaccine (ARCT-021, ARCT-154, ARCT-165, or placebo) administration and will include:
 
 Confirmation of COVID-19 symptoms Confirmation of SARS-CoV-2 infection by reverse transcriptase-polymerase chain reaction (RT-PCR) Collection of COVID-19 diagnoses made outside of study-related procedures

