4.1. Baseline Definition

For both the priming vaccination phase and booster vaccination phase, the baseline is defined as the last non-missing assessment prior to the first priming study vaccine administration. Both scheduled and unscheduled visits and assessments will be used in determining baseline. The change from baseline is calculated as the post-baseline value minus the baseline value.

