9.3. Clinical Laboratory Evaluations

Clinical chemistry and hematology will be collected at scheduled timepoints. Actual values, changes from baseline, and abnormal toxicity grading for clinical safety laboratory assessment results will be summarized by study treatment group and age group for the priming vaccination period at each timepoint using descriptive statistics. Abnormal toxicity grading is defined as a toxicity grade equal or greater than Grade 1. Shift in toxicity grades from baseline will be summarized by visit and treatment group for all participants using the frequency count and percentage of participants in each category. Shift table for Neutrophils only will also be presented by visit and treatment group for all participants and by race using the frequency count and percentage of participants in each category.

For re-enrolled subjects and the booster vaccination period, separate summaries will be produced for abnormal chemistry and hematology by toxicity grading and age group. All data will be included in data listings.

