* In addition to grading the measured local reaction at the greatest single diameter, the measurement should be recorded as a continuous variable.

** Induration/Swelling should be evaluated and graded using the functional scale as well as the actual measurement.

*** Oral temperature; no recent hot or cold beverages or smoking.

Source: DHHS 2007

Table 13-9: Toxicity Grading for Safety Laboratory Assessments

Laboratory Parameter*	Mild (Grade 1)	Moderate (Grade 2)	Severe (Grade 3)	Potentially Life-Threatening (Grade 4)**
Sodium – Hyponatremia mEq/L	132 – 134	130 – 131	125 – 129	< 125
Sodium – Hypernatremia mEq/L	144 – 145	146 – 147	148 – 150	> 150
Potassium – Hyperkalemia mEq/L	5.1 – 5.2	5.3 – 5.4	5.5 – 5.6	> 5.6
Potassium – Hypokalemia mEq/L	3.5 – 3.6	3.3 – 3.4	3.1 – 3.2	< 3.1
Glucose – Hypoglycemia mg/dL	65 – 69	55 – 64	45 – 54	< 45
Glucose – Hyperglycemia Fasting – mg/dL Random – mg/dL	100 – 110 110 – 125	111 – 125 126 – 200	>125 >200	Insulin requirements or hyperosmolar coma
Blood Urea Nitrogen BUN mg/dL	23 – 26	27 – 31	> 31	Requires dialysis
Creatinine – mg/dL	1.5 – 1.7	1.8 – 2.0	2.1 – 2.5	> 2.5 or requires dialysis
Calcium – hypocalcemia mg/dL	8.0 – 8.4	7.5 – 7.9	7.0 – 7.4	< 7.0
Calcium – hypercalcemia mg/dL	10.5 – 11.0	11.1 – 11.5	11.6 – 12.0	> 12.0
Magnesium – hypomagnesemia mg/dL	1.3 – 1.5	1.1 – 1.2	0.9 – 1.0	< 0.9
Phosphorous – hypophosphatemia mg/dL	2.3 – 2.5	2.0 – 2.2	1.6 – 1.9	< 1.6
Creatinine kinase– mg/dL	1.25 – 1.5 x ULN***	1.6 – 3.0 x ULN	3.1 – 10 x ULN	> 10 x ULN
Albumin – Hypoalbuminemia g/dL	2.8 – 3.1	2.5 – 2.7	< 2.5	--
Total Protein – Hypoproteinemia g/dL	5.5 – 6.0	5.0 – 5.4	< 5.0	--
Liver Function Tests –ALT, AST increase by factor	1.1 – 2.5 x ULN	2.6 – 5.0 x ULN	5.1 – 10 x ULN	> 10 x ULN
Bilirubin – when accompanied by any increase in Liver Function Test increase by factor	1.1 – 1.25 x ULN	1.26 – 1.5 x ULN	1.51 – 1.75 x ULN	> 1.75 x ULN
Bilirubin – when Liver Function Test is normal; increase by factor	1.1 – 1.5 x ULN	1.6 – 2.0 x ULN	2.0 – 3.0 x ULN	> 3.0 x ULN
Hemoglobin (Female) - gm/dL	11.0 – 12.0	9.5 – 10.9	8.0 – 9.4	< 8.0
Hemoglobin (Female) change from baseline value - gm/dL	Any decrease – 1.5	1.6 – 2.0	2.1 – 5.0	> 5.0
Hemoglobin (Male) - gm/dL	12.5 – 13.5	10.5 – 12.4	8.5 – 10.4	< 8.5
Hemoglobin (Male) change from baseline value – gm/dL	Any decrease – 1.5	1.6 – 2.0	2.1 – 5.0	> 5.0
WBC Increase - cell/mm ³	10,800 – 15,000	15,001 – 20,000	20,001 – 25,000	> 25,000

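### Laboratory change and grade shift after Dose 2 and the booster are measured only from the pre-Dose 1 value; same-dose reference tables should be added, chiefly for haemoglobin change

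*SAP*

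**What the plan says.** SAP 2.1 lists, under the primary safety objective for priming, "Safety laboratory assessment before and 7 days after each study vaccine administration, by toxicity grade", to be summarised for each vaccination. SAP 2.3 gives the booster the same form as an exploratory endpoint: "Safety laboratory assessment prior to and 7 days after booster vaccine administration by toxicity grade".

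SAP 4.1 covers both phases with one rule: "the baseline is defined as the last non-missing assessment prior to the first priming study vaccine administration". It adds that "The change from baseline is calculated as the post-baseline value minus the baseline value".

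For the priming period, SAP 9.3 plans actual values, changes and abnormal grades at each timepoint, and "Shift in toxicity grades from baseline will be summarized by visit and treatment group for all participants". For the booster period and for re-enrolled participants it plans only summaries of abnormal grades.

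The toxicity scale in SAP 13.8 (Table 13-9) contains a row "Hemoglobin (Female) change from baseline value - gm/dL" and a matching row for men. In both, any decrease up to 1.5 g/dL is Grade 1 and 1.6 to 2.0 g/dL is Grade 2. Protocol 1.5 already reports "declining hemoglobin values (most likely due to blood sampling during trial participation".

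**The concern.** The endpoint is organised around each injection, but the reference value is not. The Day 35 result, 7 days after Dose 2, is set against Day 0. The Day 215 result, 7 days after the booster, is set against a value nominally 215 days old. Whatever happened between Day 0 and the dose in question is mixed with what happened in the 7 days after it.

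For most analytes this affects only the change and shift tables. For haemoglobin change it also affects the grade, because the grade is defined by the fall from baseline. What is at stake is how well the final report can describe laboratory tolerability of Dose 2 and of the booster as separate doses.

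**Working it through.** **Samples available.** The schedules of events (Protocol Appendix 1, SAP Appendix 1) place safety blood on Days 0, 7, 28, 35, 208 and 215, taken before injection on dosing days. A same-dose reference therefore exists for every dose.

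**Scheduled draw days from the reference sample to the graded sample** (safety, antibody and CMI draws, counting the reference day):

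| Graded sample | Pre-Dose 1 reference | Same-dose reference |
|---|---|---|
| Day 7 | 1 (Day 0) | 1 (Day 0) |
| Day 35 | 4 (Days 0, 7, 14, 28) | 1 (Day 28) |
| Day 215 | 8 (Days 0, 7, 14, 28, 35, 42, 56, 208) | 1 (Day 208) |

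Days 56 and 208 are 208 − 56 = 152 days apart, with no scheduled draw between them.

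**Which grades depend on baseline.** In Table 13-9, only the two haemoglobin-change rows do. All other rows, including the separate haemoglobin-level rows, use absolute cut-offs, multiples of the upper limit of normal or clinical criteria.

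**Illustration.** The plan states no figure to reproduce. Assumptions, none from the documents: the within-person haemoglobin decrease is normal with mean d and SD s, recorded to 0.1 g/dL. A recorded fall of at least 0.1 then means a true fall above 0.05, and at least 1.6 means above 1.55.

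- P(Grade ≥1) = Φ((d − 0.05)/s)
- P(Grade ≥2) = Φ((d − 1.55)/s)

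With s = 0.5 g/dL and no vaccine effect:

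| Mean fall d (g/dL) | Grade ≥1 | Grade ≥2 |
|---|---|---|
| 0 | Φ(−0.1) = 46.0% | Φ(−3.1) = 0.10% |
| 0.2 | Φ(0.3) = 61.8% | Φ(−2.7) = 0.35% |
| 0.5 | Φ(0.9) = 81.6% | Φ(−2.1) = 1.79% |

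A same-dose reference still leaves the dosing-day draw. If that leaves d = 0.1, Grade ≥1 is Φ(0.1) = 54.0%, not 46%.

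Over a wider grid (s from 0.4 to 0.8, accumulated fall 0.2 to 0.6), the pre-Dose 1 reference gives Grade ≥1 in 57% to 92%, against 53% to 55% with a remaining fall of 0.1. The excess is about 5 to 37 percentage points, the same in placebo and active arms.

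**Effect on the comparison with placebo.** With equal draws and no vaccine effect, the arm difference is zero under either reference. With an assumed true effect of 0.2 g/dL and s = 0.5, the Grade ≥1 difference is:

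- fall 0.1: Φ(0.5) − Φ(0.1) = 69.1% − 54.0% = 15.2 points (before rounding);
- fall 0.5: Φ(1.3) − Φ(0.9) = 90.3% − 81.6% = 8.7 points.

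The dilution applies to Grade ≥1. At Grade ≥2 the model moves the other way: at s = 0.6 the difference is 1.1 points with a fall of 0.1 and 4.9 points with a fall of 0.6.

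**The case against.** The strongest reply is that the endpoint asks for grades at two times and names neither a reference value nor a within-participant change. SAP 9.3 shows grades at each priming timepoint, so Day 28 and Day 35 both appear. For participants with both samples, the mean change from Day 28 to Day 35 is the difference of the two mean changes from Day 0. A fixed pre-treatment baseline with a concurrent placebo arm is a legitimate design. Day 28 is itself post-treatment, so using it as the only reference could hide a persisting Dose 1 effect.

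Most of this stands: the plan does not contradict its endpoint, and Day 0 should not be displaced. But counts at each visit do not show which participants worsened after a dose, and the Day 28 and Day 35 haemoglobin-change grades are both measured from Day 0.

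A reader might infer several stronger points that the documents do not support:

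- **Blood loss is counted as vaccine toxicity.** The objective is "To assess the safety and reactogenicity of ARCT-021 compared to placebo for priming vaccination", all priming arms share one draw schedule, and the note to Protocol Table 13-6 applies grades without regard to the investigator's view of clinical significance. Grade counts rise in every arm; no false difference between randomised arms follows.
- **All Dose 2 and booster grades are affected.** Only the haemoglobin-change rows are.
- **Booster-period falls reflect blood sampling.** The 152-day gap without a scheduled draw does not support that. The issue at Day 215 is simply an old reference.
- **The Phase 3 dose choice is distorted.** That choice was made by protocol version 4.0 (Protocol 1.6 and 7.8), before this SAP.

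**Conclusion.** The point holds as a limitation of the planned tables. For Dose 2 and the booster, no within-participant before-and-after laboratory change or shift is planned, although the samples exist.

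In the randomised priming comparison the consequence is limited: inflated haemoglobin-change grades in all arms and possible dilution of a Grade ≥1 difference. For scale, with 150 planned per study group (75 in each age cohort), the s = 0.5 model gives 69 participants at Grade ≥1 with no fall (150 × 0.460) and 93 to 122 with a fall of 0.2 to 0.5 g/dL (150 × 0.618 and 150 × 0.816). These counts rest wholly on the assumed SD and falls. Much of the count comes from the any-decrease rule itself.

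The gap matters more where the placebo control is weaker. Placebo-primed participants who did not re-enrol are randomised only among active boosters (SAP Table 3-1). Re-enrolled participants have no all-placebo arm in their repeated priming series. For these groups the within-person contrast is the main control. SAP 4.1 also does not say which first priming dose sets the baseline for re-enrolled participants.

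This is a cheap improvement, not a flaw that invalidates the safety analysis.

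**What to change.** Keep the pre-Dose 1 baseline and all summaries based on it. In SAP 9.3, add tables that take the last value before each dose as reference, Day 28 for Day 35 and Day 208 for Day 215 (Day 7 already uses the pre-Dose 1 value):

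- change in each analyte;
- grade from the haemoglobin-change rows;
- shift in toxicity grade.

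Present them by treatment group, beside placebo for priming and beside placebo/no booster for the booster period where those samples exist. Produce them separately for re-enrolled participants, and state in SAP 4.1 which dose sets their baseline.

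The cost is SAP wording and a few more tables; no new data are needed. Because the Day 28 and Day 208 values are post-treatment, a note should say that the new tables are to be read with the Day 0 tables, so that persisting effects of earlier doses are not hidden.
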